10.1 Study Design

This is a post-market 1:1 randomized, prospective, multi-center study with a planned analysis of 400 subjects (200 per treatment group). Details regarding the number of study sites and enrollment allocation within each site are presented above in **Section 5.1**. Details regarding sample size are presented below in **Section 10.8**.

10.2 Treatment Assignment

See section 3.4 for the assignment of planned treatment.

Treatment received is defined as KINCISE if the KINCISE device was used for femoral broaching, MALLET otherwise.

10.3 Levels of Significance

The level of significance for the hypotheses related to the non-inferiority/superiority tests of the primary endpoint and for the hypotheses associated with the secondary endpoints is defined is sections 10.9.2 and 10.9.3.

Unless otherwise stated, all other confidence intervals and p-values will be provided for exploratory analyses to facilitate clinical judgement, with no adjustment of significance levels; Confidence intervals will be 2-sided 95% confidence intervals.

10.4 Handling of Missing Data

Missing data will be assumed missing at random. Actual subject data which is collected will be utilized in analyses to determine the outcome of the analyses for all endpoints.

10.5 Primary and Secondary Endpoints

10.5.1 Primary Endpoint

The primary endpoint analysis is to demonstrate that femoral broaching time (in minutes) with KINCISE is non-inferior to femoral broaching time with manual instruments (not using KINCISE) under a non-inferiority margin of 1.25 minutes.

Hypotheses for this non-inferiority analysis are as follows:

- Null Hypothesis: $H_0: \mu_I \ge \mu_C + 1.25$
- Alternative Hypothesis: H_A : $\mu_I < \mu_C + 1.25$

where μ_I and μ_C are mean femoral broaching times with and without KINCISE, respectively, and 1.25 is the NI margin. The null hypothesis will be rejected and non-inferiority will be concluded if the 1-sided upper 95% confidence limit for the $\mu_I - \mu_C$ difference (based upon a 2-sample t-test) is less than 1.25. The study will be deemed to be successful if this analysis demonstrates non-inferiority of femoral broaching time.

If non-inferiority is successfully demonstrated, then a test for superiority will be conducted to assess if femoral broaching time with KINCISE is less than femoral broaching time without KINCISE with statistical significance (1-tailed t-test with 5% alpha).

10.5.2 Secondary Endpoints

If the primary endpoint analysis successfully demonstrates non-inferiority of femoral broaching time, regardless of whether the above test of superiority was successful or not, then the following three secondary endpoint analyses will be conducted under a gatekeeping strategy, in this specified order, where testing is performed in sequence and continues until an alternative hypothesis is not rejected or all hypotheses have been tested, each with a 1-sided alpha of 0.05:

- A non-inferiority test of skin-to-skin OR time will be conducted with a non-inferiority margin of 3.75 minutes, using a 2-sample t-test
 - Null Hypothesis: $H_0: \mu_I \ge \mu_C + 3.75$
 - Alternative Hypothesis: H_A : $\mu_I < \mu_C + 3.75$
 - where μ_I and μ_C are mean skin-to-skin OR times with and without KINCISE, respectively. The null hypothesis will be rejected and non-inferiority will be concluded if the 1-sided upper 95% confidence limit for the $\mu_I - \mu_C$ difference (based upon a 2-sample t-test) is less than 3.75.
- A non-inferiority test of the percent of subjects with acetabular cup abduction angle within +/- 10 degrees of plan under a NI margin of 10%
 - Null Hypothesis: $H_0: P_I \le P_C 10\%$
 - Alternative Hypothesis: $H_A: P_I > P_C 10\%$

Confidential Version Date: 040CT2021 DePuy Synthes Protocol DSJ_2019_03 / Version 2.0 / TV-eFRM-02920 Page **33** of **53**

- where P_I and P_C are the percentages of subjects with acetabular cup abduction angle within 10% of plan with and without KINCISE, respectively. The null hypothesis will be rejected and non-inferiority will be concluded if the 1-sided lower 95% confidence limit for the $P_I - P_C$ difference (based upon a normal approximation method) is greater than -10%.
- A non-inferiority test of the percent of subjects with acetabular cup version angle within +/- 10 degrees of plan under a NI margin of 10%
 - Null Hypothesis: $H_0: P_I \le P_C 10\%$
 - Alternative Hypothesis: $H_A: P_I > P_C 10\%$
 - where P_I and P_C are the percentages of subjects with acetabular cup version angle within 10% of plan with and without KINCISE, respectively. The null hypothesis will be rejected and non-inferiority will be concluded if the 1-sided lower 95% confidence limit for the $P_I - P_C$ difference (based upon a normal approximation method) is greater than -10%.

In addition, the following secondary endpoints do not have prospectively planned hypotheses; these will be summarized for both treatment groups:

- Harris Hip Score (HHS) and HHS change from preoperative baseline
- Forgotten Joint Score (FJS) and FJS change from 6-week postoperative baseline
- EQ-5D-5L and changes in these assessments from preoperative baseline
- Pain (Groin, Thigh, and Buttock)
- Patient Satisfaction
- Post-op time when functional activities can be accomplished (return to work; self-care; etc.)
- Radiographic Outcomes (based upon: AP Hip, AP Pelvis, and Lateral)
- Length of hospital stay after index THA
- Re-hospitalizations during the study (including a specific summary of re-hospitalizations within 90 days)
- Narcotic drug usage throughout the study (patient reported)
- Complications (including a specific summary of complications within 90 days post-surgery)

10.6 Analysis Sets

Population	Subjects Included
Enrolled Population	The Enrolled population set will consist of all subjects who sign the informed consent document.
Safety Population	The Safety Population set will consist of all subjects in the Enrolled population set for whom treatment was attempted, according to the actual treatment received.
Per Protocol Population	The Per Protocol Population set will consist of all subjects in the Enrolled population set who successfully received the planned treatment, who were seen at least once at a post-operative visit, and who did not have any protocol deviations which were prospectively determined to potentially have influence on the scientific validity of the data (such as inclusion/exclusion criteria).

Table 10-1 Analysis Populations

10.8 Sample Size Justification

Primary endpoint NI analysis: Based upon input from key opinion leaders (KOLs) and data from other studies, typical femoral broaching time with manual instruments is anticipated to have a range of 5 to 15 minutes, which implies a standard deviation of approximately 2.5 minutes (1/4 of the range). Moreover, KOLs suggest that a difference of 10 minutes in femoral broaching time (increase for a single patient) is clinically meaningful. The non-inferiority margin of 1.25 minutes was established because it is ½ of the anticipated standard deviation and is much less than a clinically meaningful difference. Under a 1-sided test with 5% alpha, a sample size of N=88 per group would be sufficient to demonstrate non-inferiority with 95% power. A sample of size N=200 per group (N=400 total) was chosen as feasible by the sponsor and desirable for providing further data for both KINCISE and Anterior Advantage; this sample size would provide more than 99% power to demonstrate non-inferiority for the primary endpoint analysis.

Primary endpoint supplemental superiority analysis: It is not known if there will be a true difference in means between groups. However, if there is a true difference of 1 minute between group means (lower time favoring KINCISE), and assuming an SD as stated above (2.5 minutes), then a sample of N=200 per group (N=400 total) would provide approximately 99% power to demonstrate superiority.

Secondary endpoint analyses:

Non-inferiority of skin-to-skin OR time

Based upon input from KOLs and data from other studies, skin-to-skin OR time is anticipated to have a typical range from 60 to 90 minutes, which implies a standard deviation of approximately 7.5 minutes (1/4 of the range). The non-inferiority margin of 3.75 minutes was established because it is ½ of the anticipated standard deviation and is much less than the 10 minute clinically meaningful difference in femoral broaching time (a subset of skin-to-skin OR time). Under a 1-sided test with 5% alpha, a sample size of N=200 per group would be sufficient to demonstrate non-inferiority with greater than 99% power.

Non-inferiority of optimal acetabular cup abduction

The percent of subjects within +/- 10 degrees of planned cup abduction for an anterior approach (AA) is anticipated to be between 90% and 95% (based on studies presented by Hamilton¹² and Rathod¹³, respectively). These are a clinical improvement from percentages exhibited with a posterior approach (PA), which were 79% and 86% in [1] and [2], respectively. A NI margin of 10% was chosen because it is less than the improvement from PA to AA observed by Hamilton¹² and Rathod¹³. With this margin and a 1-sided test with 5% alpha, a sample size of N=200 per group would be sufficient to demonstrate non-inferiority with approximately 95% power.

Non-inferiority of optimal acetabular cup abduction

The percent of subjects within +/- 10 degrees of planned cup version for an anterior approach (AA) is anticipated to be between 91% and 92% (based on studies by Rathod¹³ and Hamilton¹², respectively). These are a clinical improvement from percentages exhibited with a posterior approach (PA), which were 64% and 77% in [1] and [2], respectively. A NI margin

of 10% was chosen because it is less than the improvement from PA to AA observed by Hamilton¹² and Rathod¹³. With this margin and a 1-sided test with 5% alpha, a sample size of N=200 per group would be sufficient to demonstrate non-inferiority with approximately 95% power.

In summary, with a sample size of N=400 (200 with KINCISE; 200 without KINCISE), the anticipated overall likelihood of demonstrating the primary endpoint non-inferiority analysis, followed by the three stated secondary endpoint non-inferiority analyses in the specified gate-keeping order, is at least $(99\%)(95\%)(95\%) \approx 88\%$.

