10.9.4 Secondary Endpoints

All secondary endpoint analyses will be performed on the Per Protocol Population.

Skin-to-skin OR time in minutes will be summarized as a continuous endpoint for both treatments. The difference in means $\mu_I - \mu_C$ will also be summarized as a continuous endpoint. Its 1-sided upper 95% confidence limit and the p-value for the test of non-inferiority with a margin of 3.75 based on a 2-sample t-test will be produced if the alternative hypothesis of non-inferiority of the primary endpoint is rejected.

The difference between acetabular cup abduction angle and plan for each subject will be summarized as a continuous endpoint for both treatments. The proportion of subjects with acetabular cup abduction angle within 10% of plan will be summarized as a categorical endpoint for both treatments. The difference in proportions $P_I - P_C$ will also be summarized as a categorical endpoint. Its 1-sided lower 95% confidence limit and the p-value for the test of non-inferiority with a margin of 10% based upon a normal approximation method will be produced if the alternative hypothesis of non-inferiority of skinto-skin OR time is rejected.

The difference between acetabular cup version angle and plan for each subject will be summarized as a continuous endpoint for both treatments. The proportion of subjects with acetabular cup version angle within 10% of plan will be summarized as a categorical endpoint for both treatments. The difference in proportions $P_I - P_C$ will also be summarized as a categorical endpoint. Its 1-sided lower 95% confidence limit and the p-value for the test of non-inferiority with a margin of 10% based upon a normal approximation method will be produced if the alternative hypothesis of non-inferiority of acetabular cup abduction angle within 10% of plan is rejected.

With no prospectively planned hypotheses, the following secondary endpoints will be summarized at all visits with available data for both treatments as continuous variables:

- The Harris Hip Score (HHS) and change from baseline HHS
- Forgotten Joint Score (FJS) and change from 6-week postoperative FJS
- EQ-5D-5L and change from baseline
- Pain (Groin, Thigh, and Buttock)
- Patient Satisfaction
- Radiographic Outcomes (based upon: AP Hip, AP Pelvis, and Lateral)
- Length of hospital stay after index THA

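### The 10-point cup-abduction margin exceeds one of the two improvements said to justify it, and both cup endpoints are formally defined in percent where degrees are meant

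*Protocol*

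**What the plan says.** **Margin.** For cup abduction, Protocol 10.8 says the proportion "within +/- 10 degrees of planned cup abduction for an anterior approach (AA) is anticipated to be between 90% and 95" percent, citing two studies in that order. It compares these with "percentages exhibited with a posterior approach (PA), which were 79% and 86% in [1] and [2], respectively". The margin then rests on one sentence: "A NI margin of 10% was chosen because it is less than the improvement from PA to AA observed" in those two studies. SAP 7 repeats the passage. The same sentence supports the version margin, with anterior rates of 92% and 91% against posterior rates of 64% and 77% (first and second cited study).

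**Endpoint definition.** Protocol 10.5.2 introduces the abduction test as one on the "percent of subjects with acetabular cup abduction angle within +/- 10 degrees of plan under a NI margin of 10" percent. The clause under the hypotheses then says that P_I and P_C "are the percentages of subjects with acetabular cup abduction angle within 10% of plan with and without KINCISE, respectively". For version they "are the percentages of subjects with acetabular cup version angle within 10% of plan with and without KINCISE, respectively". SAP 8.8.2 and 8.8.3 carry the same mismatch. In Protocol 10.9.4 only the percent wording is used: "The proportion of subjects with acetabular cup abduction angle within 10% of plan will be summarized as a categorical endpoint for both treatments", and likewise "The proportion of subjects with acetabular cup version angle within 10% of plan will be summarized as a categorical endpoint for both treatments". Its condition for going on to the version test repeats the percent wording.

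SAP Table 10.1 corrects a different slip in Protocol 10.5.2 (which hypothesis is rejected) but not this one.

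**The concern.** Both tests are formal and alpha-controlled, so each needs a threshold with a true rationale and a single definition of success.

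The plan sets its own standard for the abduction margin: it should be smaller than the gain from posterior to anterior approach. If the margin is larger than that gain in one of the two sources, a non-inferiority claim can be made while the data still allow the whole gain to be lost by that source's measure.

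For the definition, the quantities in the hypotheses are P_I and P_C. The clause that defines them contradicts the statement of the test, and a program written from that clause would count far fewer cups as successes. Only abduction and version are at stake. An abduction failure would block version and nothing else.

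**Working it through.** **Inputs** (Protocol 10.8, SAP 7): 200 per arm, one-sided alpha 0.05, margin 0.10, unpooled normal approximation. SE = sqrt(P_I(1-P_I)/200 + P_C(1-P_C)/200). Power = Phi((P_I - P_C + 0.10)/SE - 1.645).

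**1. The plan's own power.** At 90% in both arms, SE = sqrt(2 x 0.90 x 0.10/200) = 0.030 and power = Phi(3.333 - 1.645) = 95.4% (exact binomial 95.2%). The stated figure of about 95% reproduces. At 95% it is 99.8%; for version it is 96.8% at 91% and 97.9% at 92%.

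**2. The rationale, by subtraction.**

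| Endpoint | First cited study | Second cited study | Margin below both? |
|---|---|---|---|
| Abduction | 90 - 79 = 11 | 95 - 86 = 9 | No |
| Version | 92 - 64 = 28 | 91 - 77 = 14 | Yes |

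The bracketed citation numbers match the SAP reference list but not the Protocol's. Pairing the abduction figures the other way gives 90 - 86 = 4 and 95 - 79 = 16, so one study is still below 10.

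**3. What the 10-point margin allows.**

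- True loss of 9 points (86% vs 95%): SE = 0.0290; Phi(0.01/0.0290 - 1.645) = 9.7% declared non-inferior (exact 10.4%).
- True loss of 11 points (79% vs 90%): SE = 0.0358; Phi(-0.01/0.0358 - 1.645) = 2.7% (exact 2.9%).
- True loss of 10 points (85% vs 95%, or 80% vs 90%): 5.0%, as designed.
- Control observed at 95%: solving d + 1.645 x SE = 0.09 and = 0.10 gives d = 0.047 and 0.056. Observed deficits of about 4.7 to 5.6 points therefore pass without excluding a 9-point loss. Example: 190/200 vs 180/200 gives -0.050 - 1.645 x 0.0262 = -0.0931.
- Equal observed rates: the lower limit is -4.9 points at 90% and -3.6 points at 95%, and both exclude a 9-point loss.
- No true difference: the exact chance of a limit between -10 and -9 points is 4.2% at 90% success and 0.6% at 95%.

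**4. The percent clause read literally.** The documents give no planned angles. Assume plans of 35 to 50 degrees for abduction and 10 to 25 degrees for version, with normal errors centred on plan. The SD that puts a share s within 10 degrees is 10/z((1+s)/2), with z(q) the standard normal quantile.

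| | Abduction | Version |
|---|---|---|
| SD in degrees (s) | 6.08 (90%), 5.10 (95%) | 5.90 (91%), 5.71 (92%) |
| Window at 10% of plan, degrees | 3.5 to 5.0 | 1.0 to 2.5 |
| Success, 2 x Phi(window/SD) - 1 | 44% to 67% | 14% to 34% |
| Power, 10-point margin | 64% to 69% | 90% down to 68% |

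This applies only if the clause were programmed as written.

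**The case against.** The strongest reply is that no planned number or decision changes. The power is right, study success depends on the primary endpoint alone, and the rationale misses by one point in one of two sources. A pass rate of 9.7% at a 9-point loss is how any test behaves inside its margin. The 4.2% figure uses a 90% success rate, which belongs to the study with the 11-point gain; at the 95% rate of the 9-point study it is 0.6%. Both arms use the anterior approach, so the posterior-to-anterior gap is an external benchmark. On units, degrees appear in the test statements, the sample-size text, the SAP summary bullets and SAP 8.8.4, so nobody is likely to misread the clause, and the literal-reading power describes an analysis nobody intends.

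Much of this stands. The test works as designed at its margin, the exposure is small when there is no true difference (0.6% is the better-matched figure), and the literal-reading power is conditional and carries no weight in the conclusion. Two things remain. The plan itself chose that benchmark as the sole support for the margin, and the claim made from it is untrue. And although the SAP bullets use degrees, the clause defining the tested proportions still says percent for both angles in both documents.

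**Conclusion.** Both errors hold and should be fixed. The abduction margin of 10 points is below the improvement in one cited study (11) and above it in the other (9). This follows by subtraction from the plan's own figures, and no pairing of the rates removes it. The consequence is narrow: only a pass with a lower limit between -9 and -10 points fails to exclude loss of the full 9-point improvement. The version margin is properly supported.

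The percent definition contradicts the stated test for both angles. Degrees is evidently intended, and the powered rates are already for 10 degrees, so correcting it changes no power figure. The primary endpoint, sample size and stated power are unaffected. The size of any effect from the literal reading rests on assumed planned angles and error distributions.

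**What to change.** 1. In Protocol 10.8 and SAP 7, state that 10 points is below the abduction improvement in one cited study (11) and above it in the other (9), and that a pass with a lower limit between -9 and -10 points would not exclude loss of the full 9-point improvement.
2. In Protocol 10.5.2 and 10.9.4 and SAP 8.8.2 and 8.8.3, define the success window as 10 degrees either side of plan wherever it now reads as a percentage. If only the SAP is amended, list the change in SAP Table 10.1; if both documents are corrected, no entry is needed.

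The cost is text edits. Margin, alpha, sample size and decision rule can stay. Changing the margin is optional and would mean restating the power. As an illustration, 9 points with 200 per arm gives 91.2% power at 90% success (241 per arm would be needed for 95%), and the overall figure becomes 0.99 x 0.99 x 0.912 x 0.95, or about 85% in place of 88%.

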10.9 Analysis Plan

Standard descriptive summaries for continuous data include the number of observations with data, number of observations with missing data, mean, standard deviation, median, minimum, and maximum values. For categorical data, the count (numerator), denominator and percent will be provided. Percentages will be based on the number of subjects without missing data, unless indicated otherwise.

Datapoints will be reported based on the visit date reported by the investigator. In the case where there are multiple visits reported within the same interval, the latest visit (most proximal to date of surgery) will be used for the preoperative timepoint, and the earliest visit will be used for the 6-week timepoint, and the latest (furthest from date of surgery) for the 24-week timepoint. If data is reported before the preoperative window (before -180 days pre-surgery) or after the close of the 24-week window (after 200 days post-surgery), these data will be removed from analysis and a separate analysis will report on the number of such visits.

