4.1 Primary Objective, Endpoint, and Associated Hypotheses

The primary endpoint is the mean femoral broaching in minutes collected intraoperatively. Femoral broach time should be collected intraoperatively in minutes and seconds and should begin at the time the box osteotome first enters the femoral canal and end with seating of the final broach trial within the femoral canal.

The primary objective of this study is to demonstrate that the mean femoral broaching time with KINCISE is non-inferior to the mean femoral broaching time with manual instruments when used in THA with Anterior Advantage.

If non-inferiority is successfully demonstrated then the study will be deemed successful, and a test for superiority for mean femoral broaching time will be conducted.

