7.3 Six Week Postoperative Evaluation (Day 14 – Day 60)

The following data will be collected from six-week postoperative evaluation:

- Study Visit (CRF detailing type of visit and subject status)
- Postoperative Hip Evaluation (HE2)
- Postoperative Hip Evaluation Functional Outcomes (HE3*)
- Narcotic Drug Use (patient reported)
- Harris Hip Score
- Radiographs (AP Hip (unilateral), AP Pelvis (bilateral), and Lateral)
- EQ-5D-5L
- Forgotten Joint Score
- Adverse Event Form (if needed)
- Protocol Deviation Form (if needed)
- Device Deficiency (if needed)
- End of Study (Withdrawal) Case Report Form (if needed)

* The Functional Outcomes portion of the Hip Evaluation CRF (HE3) will be initially completed at the 6 week visit, and only questions that are marked as "still cannot do" or "still have not returned to work" will be addressed at subsequent study visits

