7.4 Twenty-Four Week Postoperative Evaluation (Day 61 to Day 200)

The following data will be collected from twelve-week postoperative evaluation:

- Study Visit (CRF detailing type of visit and subject status)
- Postoperative Hip Evaluation (HE2)
- Postoperative Hip Evaluation Functional Outcomes (HE3*)
- Narcotic Drug Use (patient reported)
- Harris Hip Score
- Radiographs (AP Hip (unilateral), AP Pelvis (bilateral), and Lateral)

EQ-5D-5L

Confidential Version Date: 040CT2021 DePuy Synthes Protocol DSJ_2019_03 / Version 2.0 / TV-eFRM-02920

- Forgotten Joint Score
- Adverse Event Form (if needed)
- Protocol Deviation Form (if needed)
- Device Deficiency (if needed)
- End of Study (Withdrawal) Case Report Form (required unless completed previously)

* The Functional Outcomes portion of the Hip Evaluation CRF (HE3) will be initially completed at the 6 week visit, and only questions that are marked as "still cannot do" or "still have not returned to work" will be addressed at subsequent study visits

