Sticker sheets were created, one set for up to 30 sites, containing treatment assignments for 120 subjects using a fixed block size of 4 and a treatment allocation ratio of 1:1. On the face of each sticker is a character in the sequence A, B, C,, X, Y, Z, AA, AB, AC,AX, AY, AZ, BA, BB, BC, etc...., BX, BY, BZ, CA, etc...

The stickers should be removed sequentially to reveal the randomization code and treatment group ('Study (Kincise)' or 'Control (Mallet)') for each consecutive consented subject that meets eligibility criteria. Peeled sticker should be placed on the screening log to document that randomization was unbiased. The planned randomization group should then be documented in the applicable source document and on the Randomization eCRF (eCRF RDM) in the database.

The assigned treatment will remain secret to site personnel until subject is found to meet all eligibility criteria; No other blinding is implemented in this study.

4 Interval Windows

The study includes the following periods: Pre-op, Operative, Immediate post-op, 6 Week, 24 Week. Intervals related to each are shown in Table 3, below.

Visit	Minimum Day	Maximum Day	Midpoint Day
Pre-Op	-180	0	
Operative	0	0	0
Immediate post-op	0	Discharge	
6 week	14	60	37
24 week	61	200	130

 Table 3
 Interval Windows for Non-Radiographic Study Visits

Time point specific data collected to satisfy the primary and secondary efficacy-related objectives will be assessed for compliance with these intervals. Only data which can be attributed to the visit intervals in Table 3 will be used in the analysis of primary and secondary endpoints. This visit will be hereafter referred to as the Analysis Visit and the originally recorded visit as the Nominal Visit. If multiple measurements fall into the pre-operative window, or into the 'Immediate post-op' post-operative window, the result collected most proximate to surgery will be utilized. For the '6 week' and '24 week' visits, if multiple measurements fall into the window will be utilized for analysis.

5 Levels of Significance

The level of significance is 95%. Primary endpoint analyses, further described in section 8.7, and secondary endpoint analyses with hypotheses, further described in 8.8, will use 1-sided 95% confidence intervals and associated p-values. Data summaries of secondary endpoints without hypotheses and of exploratory endpoints will use 2-sided 95% confidence intervals and associated p-values.

6 Analysis Sets

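### The protocol picks the earliest 6-week and latest 24-week record, and date-based windows can turn a late 6-week visit into the 24-week value; the SAP's selection rule must be reconciled

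*Protocol*

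**What the plan says.** Protocol 7.3 and 7.4, Protocol Table 0-1 and SAP Table 3 give the same windows: days 14 to 60 for 6 weeks and days 61 to 200 for 24 weeks.

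Protocol 10.9 reports data according to the investigator's visit date. If there are several visits in a window, "the earliest visit will be used for the 6-week timepoint, and the latest (furthest from date of surgery) for the 24-week timepoint". For data "after the close of the 24-week window (after 200 days post-surgery), these data will be removed from analysis"; the same sentence adds that such visits will be counted separately.

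SAP section 4 also works by date: "Only data which can be attributed to the visit intervals in Table 3 will be used in the analysis of primary and secondary endpoints". The visit so derived is the Analysis Visit, as distinct from the Nominal Visit originally recorded. Table 3 prints a midpoint day of 37 for 6 weeks, and its 24-week row reads "24 week 61 200 130". The sentence on multiple 6-week or 24-week records runs "if multiple measurements fall into the window will be utilized for analysis" in the text supplied, and the words that would name the chosen record are absent. SAP section 10, which lists substantive changes from the protocol, has no entry on visit selection.

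SAP 8.1 makes the 6-week record the baseline for the Forgotten Joint Score (FJS).

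**The concern.** The outcomes are labelled 6-week and 24-week, but the protocol's rule does not aim at either time. At 6 weeks it favours the record closest to surgery, and at 24 weeks the one furthest from it. Placement by date adds a second route to a mislabelled value, because a late 6-week visit changes its label.

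The outcomes exposed are the Harris Hip Score, FJS, EQ-5D-5L and the hip evaluation items, including pain. If these are still changing during recovery, a record taken well away from its named week shifts the reported level and adds spread. FJS change is exposed at both ends. SAP 8.13 plans no sensitivity analyses and neither document plans a table of actual visit day, so the timing behind each summary would not be visible.

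**Working it through.** **Inputs.** Windows 14–60 and 61–200 (Protocol 7.3 and 7.4; SAP Table 3). Selection rule: earliest, then latest (Protocol 10.9). Named days are taken as weeks × 7: 6 × 7 = 42 and 24 × 7 = 168. Neither document prints 42 or 168 as a target, so this is an assumption; Protocol 2.1 does equate 24 weeks with 6 months.

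**The plan's own figures.** (14 + 60)/2 = 37 and (61 + 200)/2 = 130.5, printed as 130. The midpoints are the correct centres of the windows. They lie 42 − 37 = 5 days and 168 − 130 = 38 days before the named weeks.

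**Reach of the windows around the named day.**
- 6 weeks: 42 − 14 = 28 days early, 60 − 42 = 18 days late.
- 24 weeks: 168 − 61 = 107 days early, 200 − 168 = 32 days late.

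**Selection among several records in one window.**

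| Record days | Protocol 10.9 uses | Nearest to named week |
|---|---|---|
| 14 and 42 | 14 | 42 |
| 32 and 42 | 32 | 42 |
| 168 and 200 | 200 | 168 |
| 63 and 168 | 168 | 168 |

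Over every possible pair of days, weighted equally and with ties given to the earlier record, the two rules choose differently in 68% of 1,081 pairs at 6 weeks and 11% of 9,730 pairs at 24 weeks. This compares the rules only; it does not predict how often records will be affected.

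**Placement by date.** Suppose the 6-week visit takes place on day 63 (63/7 = 9.0 weeks) and the 24-week visit on day 205, with no other records.
- Days 14–60 are empty, so there is no 6-week value.
- Day 63 is the only record in days 61–200, so it is reported as 24-week.
- Day 205 is after day 200, so it is removed from analysis and counted.

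If the 24-week visit had been on day 168, the protocol's rule would have chosen it over day 63. The relabelled value therefore stands only when it is alone in the window.

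**FJS change interval.** Shortest: 61 − 60 = 1 day. Longest: 200 − 14 = 186 days. Nominal: 168 − 42 = 126 days.

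**Outcomes outside the problem.** On timing of the primary endpoint, Protocol 4.1 says "The primary endpoint is the mean femoral broaching in minutes collected intraoperatively". Skin-to-skin OR time is also operative. SAP Table 3 is headed as applying to non-radiographic visits, so it does not establish any effect on the two cup-angle tests.

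**The case against.** The best defence is that the plan defines visits by windows, not by target days, so a day-14 visit is compliant. One visit is scheduled per window, so the selection rule acts only when there are extra records. The rules are the same in both arms, and the affected outcomes carry no planned hypotheses. All of this stands and it limits the weight of the point. It does not explain why a rule should prefer day 14 to day 42 when both are available for a result labelled 6-week.

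A reader might infer more than the documents support, in four ways.

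- **That the SAP uses nearest-to-midpoint and so contradicts the protocol.** If that were the rule, a record on any of days 93 to 167 would beat day 168, because |d − 130| < 38. It is a plausible guess: midpoints are printed for the 6-week and 24-week visits but left blank for the pre-operative and immediate post-operative windows, which have their own stated rule. But no sentence gives the column that use, and the missing words may simply have been lost in reading the PDF. They could state the protocol's rule.
- **That the latest-record rule produces 9-week values at 24 weeks.** It works against them. The cause is the wide window, shared by both documents, combined with placement by date.
- **That late visits disappear unrecorded.** Protocol 10.9 commits to counting them.
- **That the treatment comparison is biased.** The study is open-label, so equal visit timing in the two arms cannot be assumed, but nothing in the documents shows unequal timing.

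**Conclusion.** The point holds as a minor one. The protocol's stated rule selects off-target records whenever a window holds several, and placement by date lets a 6-week visit held on day 61 or later become the 24-week value when it stands alone. The FJS change interval can range from 1 to 186 days against 126.

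The reach is confined to descriptive secondary outcomes: Harris Hip Score, FJS, EQ-5D-5L and the hip evaluation. The primary endpoint and OR time are untouched, and no effect on the cup-angle tests is shown. The documents do not say how many subjects would have several records in a window or a late 6-week visit, so the effect on any reported mean cannot be sized.

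Whether the SAP follows the protocol's selection rule cannot be settled from the text supplied. The two must be reconciled, but a contradiction is not established. The conclusion assumes that the 6-week and 24-week labels mean days 42 and 168.

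**What to change.** Put one rule in both documents and complete the SAP sentence to match:

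1. Among records in the window, use the one closest to day 42 for 6 weeks or day 168 for 24 weeks, with a stated tie-break. Replace the Table 3 midpoints by these days, or state that the column does not select records.
2. Do not let a record whose nominal visit is 6-week serve as the 24-week value.
3. Tabulate actual visit day by arm for both visits.
4. Beyond the count already planned, summarise 24-week visits after day 200 supportively.
5. Correct the opening line of Protocol 7.4, which calls the day 61 to 200 visit a twelve-week evaluation under a 24-week heading.

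The cost is wording in both documents and a small programming change. A few late 6-week visits will no longer fill a missing 24-week value. A sole early record inside the window, such as day 14, will still be used, but the visit-day table will show it.
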